4. CHANGES IN THE PLANNED ANALYSIS OF THE STUDY

Deviating from Section 7.3.4 in the CTP laboratory data will be analysed on normalised values.

If for some reason $AUC_{0-\infty}$ can not be calculated, AUC_{0-tz} will be used instead as the primary endpoint.

The PK analysis of absolute bioavailability will also be performed for the comparison T3/R. This will be done in the same way as the comparisons of T1 and T2 with R, which is described in Section 7.3.1 of the CTP.

All other analyses described in this TSAP are in accordance with the statistical methods described in the revised CTP.

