2	24:00	08:00	Breakfast (voluntary) ³ , discharge from trial site	x	x	x	x	x		
FU	6	3 to 7			End of trial (EOS) examination ⁴		x	x	x	x

1. Subject must be informed and written informed consent obtained prior to starting any screening procedures. Screening procedures include physical examination, check of vital signs, ECG, safety laboratory (including drug screening), demographics (including determination of body height and weight, smoking status and alcohol history), relevant medical history, concomitant therapy and review of inclusion/exclusion criteria. Pharmacogenetic samples will be collected if needed.
 2. The time is approximate; the procedure is to be performed and completed within the 3 h prior to drug administration.
 3. If several actions are indicated at the same time, the intake of meals will be the last action.
 4. At the end of trial visit the EoTrial examination includes physical examination, vital signs, ECG, safety laboratory, recording of AEs and concomitant therapies.
 5. Only urine drug screening and alcohol breath test will be done at this time
 6. AEs and concomitant therapies will be recorded throughout the trial, but will be specifically asked for at the times indicated in the Flow Chart above.
 7. Serum electrolytes only
- * At Visit 5/period 4 all subjects receive treatment T3

FLOW CHART – INTRAVENOUS ADMINISTRATION (R)

Period	Visit	Day	Planned time (relative to drug administration) [h:min]	Approximate clock time of actual day [h:min]	Event and comment	Intravenous admin.	PK/Metabolites ^{blood}	Safety laboratory	12-lead ECG	Vital signs (BP, PR)	Questioning for AEs and concomitant therapy ⁶	
SCR	1	-21 to -1			Screening (SCR) ¹			x	x	x		
1/2/3/4 (four periods separated by a wash-out of at least 6 days)	2/3 /4	-1	-12:00	20:00	Admission to trial site (Device training if needed)			x ⁵			x	
			1	-1:00	07:00	Allocation to treatment ² (visit 2 only) (Device training if needed)		x ²	x ²	x ²	x ²	x ²
				0:00	08:00	Start of BI 1265162 administration + 240 mL fluid intake	▲					
				0:05	08:05			x				
				0:30	08:30			x				
				0:59	08:59			x				
				1:00	09:00		▼			x	x	
				1:05	09:05			x				
				1:10	09:10			x				
				1:20	09:20			x				
				1:40	09:40			x				
				2:00	10:00	240 mL fluid intake		x	x ⁷	x	x	x ⁸
				2:30	10:30			x				
				3:00	11:00			x				
				3:30	11:30			x				
				4:00	12:00	240 mL fluid intake, thereafter lunch ³		x				
				5:00	13:00			x				
				7:00	15:00			x				
				8:00	16:00	Snack (voluntary)						

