7.3.1 Primary endpoint analyses

The primary and further pharmacokinetic endpoints (refer to Section 2.1.2 and 2.2.2.1) will be calculated according to the BI SOP ‘Standards and processes for analyses performed within Clinical Pharmacokinetics/ Pharmacodynamics’ (001-MCS-36-472). The non-compartmental analysis will be performed using a validated software program such as Phoenix WinNonlin™ software (version 6.3 or higher, Certara USA Inc., Princeton, NJ, USA) or SAS® Version 9.4 (or later version).

Primary analyses

The absolute bioavailability (F) will be estimated based on different administration methods of BI 1265162. As different doses are investigated among the administration methods, the primary endpoint (see Section 2.1.2) will be dose normalized for the statistical analysis. The statistical model used for the analysis of the primary endpoint will be an analysis of variance (ANOVA) model on the logarithmic scale. That is, the dose normalized PK endpoint will be log-transformed (natural logarithm) prior to fitting the ANOVA model. This model will include effects accounting for the following sources of variation: ‘sequence’, ‘subjects within sequences’, ‘period’ and ‘treatment’. The effect 'subjects within sequences' will be considered as random, whereas the other effects will be considered as fixed. The model is described by the following equation:

$$y_{ijkm} = \mu + \zeta_i + s_{im} + \pi_j + \tau_k + e_{ijkm}, \text{ where}$$

y_{ijkm} = logarithm of dose normalized $AUC_{0-\infty}$ measured on subject m in sequence i receiving treatment k in period j ,

μ = the overall mean,

ζ_i = the i^{th} sequence effect, $i = 1, 2, 3$

s_{im} = the effect associated with the m^{th} subject in the i^{th} sequence, $m = 1, 2, 3, 4$

π_j = the j^{th} period effect, $j = 1, 2, 3$

τ_k = the k^{th} treatment effect, $k = 1, 2, 3$

e_{ijkm} = the random error associated with the m^{th} subject in sequence i who received treatment k in period j .

where $s_{im} \sim N(0, \sigma_B^2)$ i.i.d., $e_{ijkm} \sim N(0, \sigma_W^2)$ i.i.d. and s_{im} , e_{ijkm} are independent random variables.

Point estimates for the ratios of the geometric means (T_i/R , $i=1, 2$), i.e. for the absolute bioavailability F , and their two-sided 90% confidence intervals (CIs) will be provided.

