7.6 RANDOMISATION

Subjects will be randomised to one of the 3 treatment sequences (T1-T2-R-T3 or R-T1-T2-T3 or T2-R-T1-T3) in a 1:1:1 ratio. The block size will be documented in the CTR.

The sponsor will arrange for the randomisation as well as packaging and labelling of trial medication. The randomisation list will be generated using a validated system that uses a pseudo-random number generator and a supplied seed number so that the resulting allocation is both reproducible and non-predictable.

The randomisation list will contain additional blocks to allow for subject replacement (refer to Section [3.3.5](#)).

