7.4 PRIMARY ENDPOINT

7.4.1 Primary analysis of the primary endpoint

Primary analysis of the primary endpoint will be performed as defined in Section 7.3.1 of the CTP.

To assess the absolute bioavailability of the treatments, the statistical model for the primary analysis defined in the CTP is an analysis of variance (ANOVA) model on the logarithmic scale including "sequence", "period" and "treatment" as fixed effects and "subject within sequence" as random effect. Absolute bioavailability of the study treatments will be estimated by the ratios of the geometric means of (T1/R), (T2/R) and (T3/R) of the primary endpoint.

Exclusion of plasma concentrations

The ADS ADPC (PK concentrations per time-point or per time-interval) contains column variables ACEXC or ACEXCO indicating inclusion/exclusion (ACEXC) of a concentration and an analysis flag comment (ACEXCO). Exclusion of a concentration depends on the analysis flag comment ACEXCO. For example, if ACEXCO is set to "ALL CALC", the value will be excluded for all types of analyses based on concentrations. If ACEXCO is set to "DESC STATS" the value will be excluded from descriptive evaluations per planned time point/time interval. If ACEXCO contains the addition "TIME VIOLATION" or "TIME DEVIATION", the value can be used for further analyses based on actual times. If ACEXCO is set to "HALF LIFE", the value will be excluded from half-life calculation only; the value is included for all other analyses. Excluded concentration itself will be listed in the CTR associated with an appropriate flag.

Exclusion of PK parameters

The ADS ADPP contains column variables APEXC and APEXCO indicating inclusion/exclusion (APEXC) of a PK parameter and an analysis flag comment (APEXCO). All analyses based on the PKs are based on PK parameter values which are not flagged for exclusion, i.e. with APEXC equal to "Included".

Further details are given in "Noncompartmental Pharmacokinetic / Pharmacodynamic Analyses of Clinical Studies" (4) and "Description of Analytical Transfer Files and PK/PD Data Files" (5).

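### T3/R cannot be estimated with the model the SAP prescribes, because T3 is given only in period 4 and period 4 contains only T3

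*SAP*

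**What the plan says.** Protocol section 7.6 states: "Subjects will be randomised to one of the 3 treatment sequences (T1-T2-R-T3 or R-T1-T2-T3 or T2-R-T1-T3) in a 1:1:1 ratio". A footnote to the inhaled-administration flow chart adds: "At Visit 5/period 4 all subjects receive treatment T3". T3 therefore never appears in periods 1-3, and nothing else appears in period 4.

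Protocol section 7.3.1 fits an ANOVA to log dose-normalised AUC0-∞ with sequence, subject within sequence, period and treatment. Subject is random, "whereas the other effects will be considered as fixed". Period and treatment each have three levels, and ratios are given for i = 1, 2 only, so T3 is outside that model. Protocol sections 7.1, 7.2 and 7.7 nevertheless include T3/R among the ratios to be estimated.

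SAP section 4 closes the gap: "The PK analysis of absolute bioavailability will also be performed for the comparison T3/R". On method it says: "This will be done in the same way as the comparisons of T1 and T2 with R", with reference to protocol section 7.3.1. SAP section 7.4.1 restates the ANOVA with period and treatment as fixed effects and says bioavailability will be "estimated by the ratios of the geometric means of (T1/R), (T2/R) and (T3/R) of the primary endpoint". No visible text drops period for T3/R, constrains period 4, or states an assumption about period effects.

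**The concern.** The protocol's model is coherent for T1, T2 and R because these rotate through periods 1-3. Extending it to T3 needs a fourth treatment level and a fourth period level, and these coincide for every subject. Data of this form cannot separate a T3 effect from a period 4 effect.

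F after inhalation without charcoal is one of the three ratios in the main objective, and inhalation is the intended therapeutic route. As written, the analysis either gives no estimate or gives one that depends on software defaults. In the second case the ratio would stand beside T1/R and T2/R with nothing in the plan to tell the reader that it is not period-adjusted as they are.

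**Working it through.** **Inputs.** 12 subjects, 4 per sequence (protocol 7.3.1, 7.7). Sequences T1-T2-R-T3, R-T1-T2-T3 and T2-R-T1-T3 (protocol 7.6). Two-sided 90% intervals (protocol 7.2). gCV 15, 20 and 25%, with precision attained with 95% probability (protocol Table 7.7: 1).

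**1. The plan's own precision figure.** With σ² = ln(1 + gCV²), precision is exp(w), where

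w = t(0.95, df) × √(2σ²/12) × √(χ²(0.95, df)/df).

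The 3x3 crossover on periods 1-3 has 36 records and rank 16, so df = 36 − 16 = 20. The upper limits at ratio 100% are 114.07, 119.10 and 124.27, exactly as tabulated. The table is labelled for i = 1, 2, 3, but it describes a 3x3 crossover that does not contain T3.

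**2. Estimability.** The four-period design has 12 × 4 = 48 rows. Its columns are intercept 1 + sequence 3 + subject 12 + period 4 + treatment 4 = 24.

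- The period 4 and T3 columns are identical.
- The rank is 17, leaving 48 − 17 = 31 residual df.
- A contrast is estimable if appending it to the matrix does not raise the rank.

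| Contrast | Subject fixed (rank 17 of 24) | Subject random (fixed part rank 8 of 12) | Period dropped |
|---|---|---|---|
| T1 − R | estimable | estimable | estimable |
| T2 − R | estimable | estimable | estimable |
| T3 − R | **not estimable** | **not estimable** | estimable |
| T3 − T2 | **not estimable** | **not estimable** | estimable |

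In the four-period model the least squares means, averaged over periods, are not estimable for any treatment.

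**3. Using only the R and T3 records.** The expected T3 − R difference within a sequence is τ_T3 − τ_R + π_4 − π_j. Here j is the period in which that sequence receives R: 3, 1 and 2 for the sequences in the order above. The term π_4 stays attached to τ_T3 in all three.

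**4. What a silent constraint does.** Suppose period 4 is set equal to one earlier period. In units of σ²:

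- Var(mean T3) = 1/12.
- Var(mean R) = 1/12.
- Var(estimated period effect minus the average of periods 1-3) = 1/12 − 1/36 = 1/18.
- The sum is 0.222, against 2/12 = 0.167 without a period term. The SE ratio is √(0.222/0.167) = 1.15, so the SE is 15% larger.

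Changing the period chosen moves the estimate by an estimated period contrast with SE √(2σ²/12). This is 0.149 × 0.408 = 0.061 at gCV 15% and 0.246 × 0.408 = 0.101 at gCV 25%.

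**5. Noise-free illustration.** Assume true T3/R = 0.50 and log-scale period effects of 0, 0.1, 0.2 and 0.3. This drift is an assumption chosen to show the mechanism.

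| Constraint | T3/R obtained |
|---|---|
| Period 4 = period 3 | 0.50 × e^0.1 = 0.55 |
| Period 4 = period 1 | 0.50 × e^0.3 = 0.67 |
| T3 column dropped, R as reference | 1.00 |

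T1/R and T2/R stay at their true values under each constraint.

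**6. Dropping period.** R is balanced over periods 1-3, so the paired estimate is T3/R multiplied by the ratio of period 4 to the geometric average of periods 1-3. An assumed shift of ×1.10 gives ×1.10 in F, and ×0.90 gives ×0.90. The formula in step 1 gives the following precision:

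| Model for T3/R | df | gCV 15% | gCV 20% | gCV 25% |
|---|---|---|---|---|
| Paired T3 − R, no period | 11 | 1.16 | 1.21 | 1.27 |
| Four treatments, no period | 33 | 1.13 | 1.18 | 1.23 |
| Table 7.7: 1 | 20 | 1.14 | 1.19 | 1.24 |

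**The case against.** The algebra is not in dispute. The case on the other side concerns reading, hidden text and weight.

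- **Reading.** The protocol model has only three periods and three treatments, so it cannot be applied literally to T3. The SAP may mean only the general approach: dose-normalise, take logs, fit an ANOVA, back-transform, give a 90% interval. SAP section 7.4.1 defeats this reading, because it keeps period as a fixed effect and lists T3/R under that model.
- **Hidden text.** Protocol section 7.3.3 is not shown, section 7.4 appears as a heading only, and the SAP numbering has gaps. A separate T3 model could sit there. It would have to override SAP sections 4 and 7.4.1, which point to protocol section 7.3.1. The caution stands for T3 − T2: protocol section 7.2 plans that comparison with an ANOVA whose form is not visible, so the finding does not rest on it.
- **Size.** The documents give no evidence of a period effect, and single doses, washout and standardised conditions make a large one less likely. This stands. The shifts in steps 5 and 6 are conditional illustrations and do not predict the error.
- **Weight.** The trial is exploratory, has no formal test, and its title discloses that the last treatment is fixed. That tells the reader T3 was not randomised, but it does not supply a model that can estimate T3/R.

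**Conclusion.** The concern holds. Under the model in SAP section 7.4.1, T3/R is not estimable, and treating subject as random or restricting the data to R and T3 does not change that. This follows from the sequences alone and needs no assumption about the data. T1/R and T2/R are unaffected.

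The size of any resulting error is unknown, because it equals a period effect that this design cannot measure. Two statements can be made. Answers obtained by equating period 4 with different earlier periods differ by contrasts with log-scale SE 0.061 to 0.101 for gCV 15 to 25%. Without a period term, a period 4 shift enters F in full, against a planned precision of 1.14 to 1.24. These figures assume complete data on 12 subjects and a common within-subject variance. Because the ratio belongs to the main objective, the SAP must be corrected before it is reported.

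**What to change.** Amend SAP sections 4 and 7.4.1 as follows.

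1. Fit the protocol 7.3.1 model to periods 1-3 only, for T1/R and T2/R.
2. Estimate T3/R from a separate within-subject model on log dose-normalised AUC for R and T3 without a period term: the mean paired log difference with its 90% interval on 11 df. The four-treatment ANOVA without period (33 df) is somewhat more precise if the variance is common to all treatments, but one model should be named in advance.
3. State that T3/R assumes the period 4 effect equals the average of periods 1-3, and label it as a non-randomised comparison confounded with period.
4. Report the period effects from periods 1-3 with 90% intervals, as a gauge of how large a period 4 shift might be.
5. Note that Table 7.7: 1 does not apply to T3/R. Under the paired model the corresponding precision is 1.16, 1.21 and 1.27.

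The cost is one paragraph and one extra model, with no new data and no change to T1/R or T2/R. The price is that T3/R is shown as conditional on an untestable assumption. Changing the sequences is no longer an option, since SAP section 6.5 speaks of the study as already performed.

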5. ENDPOINTS

5.1 PRIMARY ENDPOINT

The primary endpoint is a PK endpoint of BI 1265162, as defined in Section 2.1.2 of the CTP:

- *AUC_{0-∞} (area under the concentration-time curve of the analyte in plasma over the time interval from 0 extrapolated to infinity)*

If for some reason AUC_{0-∞} can not be calculated, AUC_{0-tz} will be used instead as the primary endpoint.

5.2 SECONDARY ENDPOINTS

5.2.1 Key secondary endpoints

Not applicable.

5.2.2 Secondary endpoints

Not applicable.

- *Adverse events (including clinically relevant findings from the physical examination)*

6. GENERAL ANALYSIS DEFINITIONS

6.1 TREATMENTS

For basic study information on treatments to be administered, assignment of treatment groups, and selection of doses, cf. Section 4.1.1 of the CTP.

Each subject is planned to be treated in four subsequent treatment periods, with one single dose in each treatment period:

- Test treatment 1 (T1):
BI 1265162 as oral solution
- Test treatment 2 (T2):
BI 1265162 for inhalation with activated charcoal
- Test treatment 3 (T3):
BI 1265162 for inhalation without activated charcoal
- Reference treatment (R):
BI 1265162 as infusion

Each subject is planned to be randomly allocated to one of three treatment sequences (T1-T2-R-T3 or R-T1-T2-T3 or T2-R-T1-T3), with T3 as fixed sequence. Each treatment period is separated by a washout period of at least 6 days.

For statistical analyses of AEs, vital signs and safety laboratory data the following separate analysis phases will be defined for each subject:

Table 6.1: 1 Analysis phases for statistical analysis of AEs, vital signs and safety laboratory data

Study analysis phase	Label	Start	End
Screening	Screening	Date of informed consent	Date/time of first administration of BI 1265162
On treatment	BI oral, BI inh cha, BI inh or BI iv, respectively	Date/time of first administration of the respective formulation of BI 1265162	Date/time of administration of the respective formulation of BI 1265162 + residual effect period (2 days * 24 h/day) or Date/time of administration of study drug in the next treatment period or 12:00 a.m. on day after subject's end of study participation date whatever comes first
Follow-up	F/U	End of the respective on-treatment period (see line above)	Date/time of administration of BI 1265162 in the next treatment period, if applicable, otherwise 12:00 a.m. on day after subject's end of study participation date

AE displays in CTR Section 15.3, Appendix 16.1.13.1.8.2 and Appendix 16.1.13.1.8.3 will present results for the on-treatment phase only.

In AE tables in CTR Section 15.3 (but not in Appendix 16.1.13.1.8.2 and Appendix 16.1.13.1.8.3 AE tables), the following total will be provided in addition:

- **"Total BI"**, defined as the total over all on-treatment phases involving BI

More details on the technical implementation of these analyses are provided in the ADS Plan of this TSAP.

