	2	24:00	08:00	Breakfast (voluntary) ³ , discharge from trial site	x	x	x	x	x	
FU	6	3 to 7			End of trial (EOS) examination ⁴		x	x	x	x

1. Subject must be informed and written informed consent obtained prior to starting any screening procedures. Screening procedures include physical examination, check of vital signs, ECG, safety laboratory (including drug screening), demographics (including determination of body height and weight, smoking status and alcohol history), relevant medical history, concomitant therapy and review of inclusion/exclusion criteria. Pharmacogenetic samples will be collected if needed.
2. The time is approximate; the procedure is to be performed and completed within the 3 h prior to drug administration.
3. If several actions are indicated at the same time, the intake of meals will be the last action.
4. At the end of trial visit the End of trial (EoTrial) examination includes physical examination, vital signs, ECG, safety laboratory, recording of AEs and concomitant therapies.
5. Only urine drug screening and alcohol breath test will be done at this time
6. AEs and concomitant therapies will be recorded throughout the trial, but will be specifically asked for at the times indicated in the Flow Chart above.
7. Serum electrolytes only

FLOW CHART – INHALED ADMINISTRATION (T2 AND T3)

Period	Visit	Day	Planned time (relative to drug administration) [h:min]	Approximate clock time of actual day [h:min]	Event and comment	PK/Metabolites ^{blood}	Safety laboratory	12-lead ECG	Vital signs (BP, PR)	Questioning for AEs and concomitant therapy ⁶
SCR	1	-21 to -1			Screening (SCR) ¹		x	x	x	
1/2/3/4 (four periods separated by a wash-out of at least 6 days)	2/3 /4/ 5*	-1	-12:00	20:00	Admission to trial site (Device training if needed)		x ⁵			x
		1	-1:00	07:00	Allocation to treatment ² (visit 2 only) (Device training if needed)	x ²	x ²	x ²	x ²	x ²
			-0:15	07:45	Active charcoal administration (T2 only)					
			0:00	08:00	BI 1265162 administration					
			0:02	08:02		x				
			0:03	08:03	Active charcoal administration (T2 only)					
			0:05	08:05		x				
			0:10	08:10		x				
			0:15	08:15		x				
			0:40	08:40		x				
			1:00	09:00		x				
			1:05	09:05	Active charcoal administration (T2 only)					
			2:00	10:00	240 mL fluid intake	x	x ⁷	x	x	x
			4:00	12:00	240 mL fluid intake, thereafter lunch ³	x				
			8:00	16:00	Snack (voluntary) ³	x				
			10:00	18:00		x				
		11:00	19:00	Dinner						
12:00	20:00		x				x			

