3. DESCRIPTION OF DESIGN AND TRIAL POPULATION

3.1 OVERALL TRIAL DESIGN AND PLAN

The study will be performed as a randomised, open-label, three-way crossover trial followed by a fixed treatment in healthy male subjects in order to compare BI 1265162 given as oral solution (T1) and inhaled via Respimat with activated charcoal (T2) and without activated charcoal (T3) compared to BI 1265162 given intravenous (Reference, R). The subjects will be randomly allocated to one of the treatment sequences (T1-T2-R-T3 or R-T1-T2-T3 or T2-R-T1-T3). For details, refer to Section [4.1](#).

For logistical reasons, subjects may receive the treatments on Day 1 e.g. first all subjects with oral, followed by all subjects with inhaled and last all subjects with intravenous administration. All 12 subjects will be dosed on Day 1 in a staggered fashion, e.g. 10 min in between intravenous administration. From a safety perspective it is acceptable to treat all subjects on the same calendar day: Low doses BI 1265162 have been selected to ensure that, even in case of a higher bioavailability of the planned oral dose, the expected plasma concentrations of BI 1265162 are in the range of plasma concentrations observed in First-in-Man trial 1399-0001. In that previous trial, all single doses of BI 1265162, up to 1200µg inhaled, were safe and well tolerated. No safety concerns were identified.

The doses for intravenous and/or oral administration might be adapted for PK purposes after the first treatment period (see Section [7.4](#)). In case this is needed, this will be implemented via a non-substantial amendment.

There will be a washout period of at least 6 days between the treatments, i.e. the dose in the previous treatment period and the dose in the current treatment period are separated by at least 6 days.

An overview of all relevant trial activities is provided in the [Flow Chart](#). For visit schedule and details of trial procedures at selected visits, refer to Sections [6.1](#) and [6.2](#), respectively.

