3.3.4.3 Discontinuation of the trial by the sponsor

Boehringer Ingelheim reserves the right to discontinue the trial at any time for any of the following reasons:

Failure to meet expected enrolment goals overall or at a particular trial site

New toxicological findings, serious adverse events, or any safety information invalidating the earlier positive benefit-risk-assessment. More specifically, the trial will be terminated if more than 50% of the subjects have drug-related and clinically relevant adverse events of moderate or severe intensity, or if at least 1 drug-related serious adverse event is reported

Violation of GCP, or the CTP impairing the appropriate conduct of the trial-

The sponsor decides to discontinue the further development of the investigational product

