5.2.6.2 Adverse event collection and reporting

5.2.6.2.1 AE collection

Upon enrolment into a trial, the subject's baseline condition is assessed (for instance, by documentation of medical history/concomitant diagnoses), and relevant changes from baseline are noted subsequently.

Subjects will be required to report spontaneously any AEs as well as the time of onset, end time, and intensity of these events. In addition, each subject will be regularly assessed by the medical staff throughout the clinical trial and whenever the investigator deems necessary. As a minimum, subjects will be questioned for AEs (and concomitant therapies) at the time points indicated in the [Flow Chart](#). Assessment will be made using non-specific questions such as 'How do you feel?'. Specific questions will be asked wherever necessary in order to more precisely describe an AE.

A carefully written record of all AEs shall be kept by the investigator in charge of the trial. Records of AEs shall include data on the time of onset, end time, intensity of the event, and any treatment or action required for the event and its outcome.

The following must be collected and documented on the appropriate CRF(s) by the investigator:

- From signing the informed consent onwards until an individual subject's end of trial:
 - All AEs (serious and non-serious) and all AESIs
 - The only exception to this rule are AEs (serious and non-serious) and AESIs in Phase I trials in healthy volunteers, when subjects discontinue from the trial due to screening failures prior to administration of any trial medication. In these cases, the subjects' data must be collected at trial site but will not be entered in the CRF or trial database and will not be reported in the CTR.
- After the individual subject's end of trial:

- The investigator does not need to actively monitor the subject for AEs but should only report any occurrence of cancer and related SAEs and related AESIs of which the investigator may become aware of by any means of communication, e.g. phone call. Those AEs should, however, not be reported in the CRF.

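### The AE displays named in SAP 6.1 count only events with onset within 48 h of a dose, and the SAP describes no table for the follow-up phase it defines

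*SAP*

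**What the plan says.** SAP Table 6.1: 1 splits each subject's time into screening, on-treatment and follow-up. On-treatment ends at "Date/time of administration of the respective formulation of BI 1265162 + residual effect period (2 days * 24 h/day"), or earlier if the next dose or the end of participation comes first. What follows, up to the next dose or the end of participation, is a separate labelled phase, F/U.

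SAP 6.1 then restricts three locations: "AE displays in CTR Section 15.3, Appendix 16.1.13.1.8.2 and Appendix 16.1.13.1.8.3 will present results for the on-treatment phase only". The one extra column in the Section 15.3 AE tables is Total BI, "defined as the total over all on-treatment phases involving BI".

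SAP 7.8.1 plans an overall AE summary, AE tables by treatment and by maximum intensity, and separate tables for drug-related AEs, SAEs, AESIs and other significant AEs. It describes no table for F/U.

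On the protocol side:
- Section 5.2.6.2.1 requires collection, from consent to the individual's end of trial, of "All AEs (serious and non-serious) and all AESIs".
- Section 3.3.4.3 terminates the trial on several grounds, among them "or if at least 1 drug-related serious adverse event is reported", with no time limit relative to dosing.
- Section 7.3.4 assigns AEs by time of onset, sends events after the residual effect period to follow-up, and lets the TSAP define further intervals for summaries, naming follow-up as an example.

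**The concern.** Collection runs to end of trial and the termination criterion has no time window, but the summary counts stop at 48 h. A drug-related SAE with onset 60 h after a dose would meet the termination criterion and still add nothing to the SAE or drug-related tables in Section 15.3, or to Total BI.

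The only AESI, hepatic injury, is defined by ALT, AST and bilirubin, so its timing depends on when blood is drawn. Few of the scheduled draws fall inside the window. A summary table could show zero SAEs, AESIs or drug-related AEs when one was collected, and a reader would need the listings to find it.

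**Working it through.** **Inputs**
- On-treatment length: "residual effect period (2 days * 24 h/day") from SAP Table 6.1: 1.
- Dosing interval: protocol 3.1, "There will be a washout period of at least 6 days between the treatments", which it explains as dose to dose, so at least 6 × 24 = 144 h.
- Four doses per subject, with T3 always last (protocol 3.1 and 7.6).
- "End of trial (EOS) examination" on Day 3 to 7, dosing on Day 1 at about 08:00 (flow charts).
- Full safety laboratory within 3 h before each dose, at 24 h and at end of trial; electrolytes only at 2 h (flow charts; protocol Table 5.2.3: 1).

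**Step 1. The plan's own window.** 2 × 24 = 48 h per dose; over four doses, 4 × 48 = 192 h.

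**Step 2. Time outside the window, taking the minimum washout and 08:00 clock times.**
- Between doses: 144 − 48 = 96 h, three times, which is 288 h.
- After the last dose, with the end-of-trial visit on Day d: 24(d − 1) − 48 h.
- Total from first dose to that visit: 3 × 144 + 24(d − 1) h.

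| End-of-trial day | Hours after last dose | Total h | On-treatment h | Follow-up h | Share in follow-up |
|---|---|---|---|---|---|
| 3 | 48 | 480 | 192 | 288 | 60.0% |
| 4 | 72 | 504 | 192 | 312 | 61.9% |
| 5 | 96 | 528 | 192 | 336 | 63.6% |
| 6 | 120 | 552 | 192 | 360 | 65.2% |
| 7 | 144 | 576 | 192 | 384 | 66.7% |

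A longer washout raises the share. After the last dose alone, follow-up runs from 0 h (Day 3) to 96 h (Day 7).

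**Step 3. Where the hepatic panels fall.** Each subject has eight scheduled full panels after a dose:
- four at 24 h, inside the window;
- three before the next dose, at 144 − 3 = 141 h to 144 h or later, in follow-up;
- one at end of trial, 48 to 144 h after the last dose. This is at or beyond the cut-off unless the visit is on Day 3 before the dosing clock time.

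So four of eight panels are reliably inside. If onset is dated at sampling, a hepatic AESI first shown on one of the others is assigned to follow-up.

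**Step 4. Other tabulations that might show such an event.** SAP 7.8.2 plans laboratory statistics over time by planned time point, and the 48 h sentence does not restrict them. They can show an abnormal value, but they do not count AESIs. The reference-range shift table ends at the final on-treatment value, normally the 24 h one. SAEs and drug-related AEs have no comparable second display.

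**The case against.** Four stronger readings are tempting. The documents support none of them.

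1. *Late events are missing from every AE table.* The sentence names three locations. The ClinicalTrials.gov, EudraCT and lay-summary tabulations in SAP 7.8.1 state no phase and are not tied to those locations. SAP 6.1 refers technical detail to an ADS Plan that is not in the text. A display of follow-up AEs elsewhere cannot be ruled out; the SAP simply describes none.
2. *Anything found at the end-of-trial visit is left out.* Assignment is by onset, not by detection. An AE first mentioned at that visit but with onset within 48 h of a dose is counted under that treatment.
3. *The SAP departs from the protocol.* It does not. Protocol 7.3.4 itself sends events after the residual effect period to follow-up, and it makes further summary intervals optional. The section cited there as the source of that period (1.2.6) is not in the text reviewed, so nothing here shows that two days is too short.
4. *Late events are lost or hidden.* Protocol 7.3.4 has SAEs, AESIs and other significant AEs listed separately, with no on-treatment limit. SAP 7 lists all individual values in Appendix 16.2. SAEs and AESIs go to the sponsor within 24 h, and withdrawals are reported with reasons. With 12 subjects, one late SAE in a listing is easy to see.

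It is also fair to say that elapsed time is not an event rate: after a single dose, most drug-related events may well start within 48 h.

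All of this limits the weight of the point. What remains is that a listing does not correct a summary table that reads zero, and that the SAP defines a follow-up phase for AE analysis without describing a table for it.

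**Conclusion.** The point holds as a modest one about presentation. In CTR Section 15.3 and the two named appendices, SAEs, laboratory-defined hepatic AESIs and drug-related AEs with onset more than 48 h after a dose would not be counted. On the plan as described they would appear only in listings. The time affected is 60.0% to 66.7% of the span from first dose to the end-of-trial visit, and four of eight scheduled full post-dose panels (three if that visit takes place before the dosing clock time on Day 3).

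This rests on the minimum 6-day washout, 08:00 clock times, laboratory-defined events being dated at sampling, and no unseen display already tabulating follow-up AEs. It does not affect the primary pharmacokinetic estimate and is not a contradiction between protocol and SAP. It is a cheap improvement, not a flaw that undermines the trial.

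**What to change.** In SAP 6.1, keep the 2-day residual effect period, the on-treatment columns and Total BI. Add to the Section 15.3 overall, drug-related, SAE and AESI tables:
- a follow-up column by preceding treatment;
- a total over on-treatment plus follow-up, counting each subject once, in line with the subject-based counting in SAP 7.8.1.

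Protocol 7.3.4 already permits such intervals. If another display is meant to cover follow-up AEs, naming it in SAP 6.1 would also settle the point.

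The cost is slightly longer tables, with late unrelated events shown in a separate column. A footnote should say that the follow-up columns differ in length. T3 is always last, so its follow-up to the end-of-trial visit is 0 to 96 h, against at least 96 h after each other treatment. The columns are for completeness, not for comparing treatments.
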